4.3.2 Administration of PRO

Standardization of procedure for collection of PRO is important. To minimise the bias and enhance the procedure compliance rate, it is preferable to appoint a study coordinator at each site to be responsible for HRQOL evaluation. The study coordinator instructs the subjects the standardized procedure for completing the QOLRAD. The completion method is described in the QOLRAD.

Major cautions for completing the QOLRAD are as follows.

- The questionnaire is completed by the subject himself/herself.
- Only one reply is selected for each question.
- The responses should reflect the patient's perceptions and views rather than those of family, friends, study coordinator, etc.

The study coordinator checks the questionnaire for completeness in order to reduce the amount of missing values. The checked QOLRAD is submitted to the sponsor.

4.4 Health Economic measurements and variables (Not applicable)

4.5 Pharmacokinetic measurements and variables (Not applicable)

4.6 Efficacy and pharmacodynamic measurement and variables

[Table 5](#) shows efficacy objectives and outcome variables.

Table 5 Efficacy objective and outcome variable

Objective	Outcome variable
Primary objective	
To evaluate the efficacy of D20 and D40 for 8 weeks on healing of RE in patients with RE in comparison with O20 by assessment of the following.	Presence/absence of RE at Week 8 according to LA classification
Secondary objective	
To evaluate the efficacy of D20 and D40 on healing of RE in comparison with O20 by assessment of the following.	Presence/absence of RE at Week 4 according to LA classification.
To evaluate the efficacy of D20 and D40 on GERD symptoms in comparison with O20 by assessment of presence/absence and severity of the patient-reported symptoms.	Time to sustained resolution of each GERD symptom (definition: number of days from the starting day of investigational product administration up to the first day of 7 consecutive days free of that symptom). Time to sustained resolution of all GERD symptoms (definition: number of days from the starting day of investigational product administration up to the first day of 7 consecutive days free of all symptoms). The proportion of subjects without each GERD symptom during the 7 days preceding visits at Week 1, 2, 4 and 8. The proportion of subjects without each GERD symptom or with 'Mild' GERD symptom up to 1 day during the 7 days preceding visit at Week 1, 2, 4 and 8.

4.6.1 Healing effect of RE according to LA classification

4.6.1.1 EGD

The EGD of esophagus, stomach and duodenum is performed on Visits 1, 3 and 4 in fasting condition.

As to the EGD on Visit 1, if the EGD data within 1 week before randomisation are available, they may be used with the consent of subject even though these are the results of test conducted before informed consent.

The EGD is performed by the method usually employed at each medical institution. The drug used for the pre-treatment of EGD is not recorded in eCRF. However, if other drug is used, the name of drug is recorded in eCRF.

The endoscopic findings in esophagus are scored according to the following LA classification. If the patient is diagnosed as RE, it is to be recorded in the eCRF whether the RE is first-time diagnosis or recurrent. If the RE is recurrent, the date of onset of initial RE is recorded. The presence or absence of esophageal hiatus hernia, Barrett's esophagus (3 cm or longer Barrett's epithelium), esophageal stricture, and gastric and duodenal ulcer is also checked, and the presence or absence of esophageal hiatus hernia is recorded in eCRF.

The subjects who are definitely diagnosed to have RE classified into LA classification Grade A, B, C or D based on the EGD on Visit 1 are registered (randomised). Those detected to have esophageal stricture, Barrett's esophagus (3 cm or longer Barrett's epithelium), and gastric or duodenal ulcer should not be registered (see Section 3.3.3).

LA classification

- Grade A: One (or more) mucosal break no longer than 5 mm, that does not extend between the tops of two mucosal folds
- Grade B: One (or more) mucosal break more than 5 mm long that does not extend between the tops of two mucosal folds
- Grade C: One (or more) mucosal break that is continuous between the tops of two or more mucosal folds, but which involves less than 75% of the circumference
- Grade D: One (or more) mucosal break which involves at least 75% of the esophageal circumference

Photo documentation, preferably as colour printouts, is essential as the record of endoscopic images.

For the central review of the grade of LA classification, all EGD images of all patients allocated the investigational products during the study period will be submitted to AstraZeneca K.K.. The personal information (such as the name and the medical record number) which can specify the patient should be masked before submission to AstraZeneca K.K..

4.6.1.2 Method of assessment

When no breaks in the esophageal mucosa are found by EGD, the RE will be judged as "healed". When healing of RE is verified on Visit 3, the subject will complete the study at the time point.

4.6.2 Patient-reported symptoms

4.6.2.1 Patient diary

The patient diary () is used to record the presence or absence of GERD symptoms and, if any, the intensity (severity) and frequency of symptoms during the treatment period. The investigator(s) or study coordinator instructs the subject how to complete the patient diary and asks the subject to start the diary from the day of diary distribution (at Visit 2).

The patient diary is distributed to the subjects on the scheduled visit of Visits 2 and 3 and the patient is asked to bring it on the next scheduled visit (Visits 3 and 4). The investigator(s) or study coordinator collects the diary after verifying the completion of diary by the subject as instructed. The collected patient diaries are submitted to the sponsor.

Once a day (preferably at the time of getting up) every day, the subject completes (selects) the replies to the questions about the presence or absence of GERD symptoms and the intensity the day before. However, on the starting day of diary, the subject completes (selects) the replies to the questions about the presence or absence of GERD symptoms during the 7 days before Visit 2, the intensity and frequency for the purpose of baseline symptom assessment.

Questions and replies

Questions:

Presence/absence of GERD symptoms

(Replies on the starting day of diary are for the past 7 days and those on Day 2 onward are for the day before.)

- I A burning feeling, rising from the stomach or lower part of the chest towards the neck?
- II Flow of sour or bitter fluid into mouth?
- III Central upper abdominal pain?
- IV Difficulties in swallowing?

Reply choices (the patient selects one of the following 4 grades):

Intensity of GERD symptom

- 0 No symptom.
- 1 Awareness of symptoms but easily tolerated.
- 2 Discomfort sufficient to cause interference with daily activities (meals, work, sleep, etc.).
- 3 Incapacitating, with inability to perform daily activities (meals, work, sleep, etc.).

Frequency (only on the starting day of diary):

How often did these symptoms occur in the past week?

- a) 0 day
- b) 1 day
- c) 2-3 days

d) 4-6 days

e) 7 days

4.6.2.2 Method of assessment

Only the symptom assessment by the subject himself/herself is used as an efficacy assessment item and the symptom assessment by physician is not done in this study.

4.6.3 PRO

See Section 4.3.

4.7 Safety measurements and variables

Table 6 shows safety objectives and outcome variables.

Table 6 Safety objective and outcome variable

Objective	Outcome variable
Secondary objective	
To evaluate the safety and tolerability of D20, D40 and O20 by assessment of the following.	AEs, clinical laboratory test values, vital signs (blood pressure and pulse rate)

The methods of collection of safety data are shown below.

4.7.1 AEs

4.7.1.1 Definitions

The definitions of AEs, SAEs and other significant adverse events (OAEs) are given below. It is of the utmost importance that all staff involved in the study are familiar with the content of this section. The principal investigator is responsible for ensuring this.

Adverse event

An adverse event is the development of an undesirable medical condition or the deterioration of a pre-existing medical condition following or during exposure to a pharmaceutical product, whether or not considered causally related to the product. An undesirable medical condition can be symptoms (eg, nausea, chest pain), signs (eg, tachycardia, enlarged liver) or the abnormal results of an investigation (eg, laboratory findings, electrocardiogram). In clinical studies, an AE can include an undesirable medical condition occurring at any time, including run-in or washout periods, even if no study treatment has been administered.

For cases where it could be suspected that a tissue-derived medicine has been contaminated by a pathogen, information about any of the above conditions (including infection) should be collected.

SAE

A SAE is an AE occurring during any study phase, and at any dose of the investigational product, comparator or placebo, that fulfils one or more of the following criteria:

- Results in death
- Is immediately life-threatening
- Requires in-patient hospitalisation or prolongation of existing hospitalisation (including hospitalisation for tests related to AEs), except hospitalisation that has been planned before enrolment.
- Results in persistent or significant disability or incapacity
- Is a congenital abnormality or birth defect
- Is an important medical event that may jeopardise the subject or may require medical intervention to prevent one of the outcomes listed above.

The causality of SAEs (ie, their relationship to study treatment) will be assessed by the investigator(s), who in completing the relevant eCRF must answer “yes” or “no” to the question “Do you consider that there is a reasonable possibility that the event may have been caused by any of the following – study medication – other medication?”. For further guidance on the definition of a SAE and a guide to the interpretation of the causality question, see 

Note that SAEs that could be associated with any study procedure should also be reported. For such events the causal relationship is implied as “yes”.

Other Significant Adverse Events (OAE)

OAEs will be identified by the Study Delivery Team Physician in consultation with the appropriate Global Drug Safety Physician during the evaluation of safety data for the Clinical Study Report. Significant adverse events of particular clinical importance, other than SAEs and those AEs leading to discontinuation of the subject from study treatment, will be classified as OAEs. Examples of these are marked haematological, biochemistry and other laboratory abnormalities, and certain events that lead to intervention (other than those already classified as serious), dose reduction or significant additional treatment. For each OAE, a narrative may be written and included in the Clinical Study Report.

4.7.1.2 Recording of AEs

For AEs spontaneously reported by the subject and/or in response to an open question “Have you had any health problems since the previous visit/during the study period?” asked by the investigator(s) or revealed by observation, only those occurring from initial administration to the last scheduled visit or withdrawal will be recorded at each visit.

Of SAEs and AEs leading to discontinuation of the subject from the study, those occurring during the time from informed consent to the last scheduled visit or withdrawal will be recorded at each visit.

In case any AE occurs, details (such as a description of the event, seriousness, maximum intensity, date of onset, date of resolution, outcome, action taken [investigational products], and causality with the investigational products) should be recorded in the eCRF.

(a) Abnormal findings

The investigator(s) will confirm whether clinically important values and changes from baseline on clinical laboratory or vital signs are observed or not. If any, such findings will be recorded in the specified module of eCRFs. However, if the abnormality meets any of the following criteria, the abnormality should be recorded in eCRF as AE:

- The abnormality results in discontinuation of the study.
- The abnormality meets any criterion for SAE.
- Investigator(s) insists it should be reported as an AE.

If the abnormality is associated with clinical signs and symptoms, the sign/symptom should be recorded in eCRF as AE.

If any abnormal laboratory values and vital signs considered as clinically important values or changes were observed at the time of completion or discontinuation of the study treatment, the investigator(s) will perform additional tests and follow-up until they are recovered or until the investigator(s) consider it is not necessary to be followed. However, there is no need to record the test results in the eCRF. The monitor will record the follow-up results on the monitoring visit report.

(b) EGD findings of disease under the study (RE)

The EGD findings of RE are not reported as the AEs except for those that correspond to the SAE definition (see Section 4.7.1.1), or those whose aggravation resulted in discontinuation of study.

(c) Assessment of causality

The causality of all AEs (i.e., the relationship to study treatment) will be assessed by the investigator(s), who in completing the relevant eCRF must answer “yes” or “no” to the question “Do you consider that there is a reasonable possibility that the event may have been caused by the investigational product?” A guide to the interpretation of the causality question is found in the [REDACTED]

Occurrence or aggravation of symptoms due to RE will be recorded on eCRF as AE whose causality with the investigational product is ‘None’.

As for SAEs, the causality with the study procedures and concomitant mediations will be judged.

(d) Maximum intensity

Maximum intensity of the reported AEs will be assessed according to the following scale:

- Mild (Awareness of sign or symptom, but easily tolerated)
- Moderate (Discomfort sufficient to cause interference with normal activities)
- Severe (Incapacitating, with inability to perform normal activities)

It is important to distinguish between serious and severe AEs. Severity is a measure of intensity whereas seriousness is defined by the criteria in Section 4.7.1.1. An AE of severe intensity need not necessarily be considered serious. For example, nausea that persists for several hours may be considered severe nausea, but not a SAE. On the other hand, a stroke that results in only a limited degree of disability may be considered a mild stroke but would be a SAE.

(e) Follow-up of AEs (ongoing AEs at the end of/withdrawal from treatment)

The AE information will be recorded in the eCRF until the last scheduled visit or withdrawal.

All AEs unresolved when the study is completed or at the time of withdrawal will be followed until the AE in concern is resolved or the investigator(s) decides that no further follow-up is necessary. More information about such AEs may be requested by AstraZeneca KK.

(f) Overdose

Should an overdose (accidental or deliberate) with the investigational products occur, it must be reported in accordance with the procedures described in Section 9.3, Procedures in case of overdose, regardless of whether the overdose was associated with any symptom or not. All symptoms associated with the overdose should be reported as AEs.

(g) Pregnancy

Should a pregnancy occur after randomisation, it must be reported in accordance with the procedures described in Section 9.4, Procedures in case of pregnancy. Pregnancy in itself is not regarded as an AE unless there is a suspicion that an investigational product may have interfered with the effectiveness of a contraceptive medication.

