3. STUDY PLAN AND PROCEDURES

3.1 Overall study design and flow chart

This Clinical Study Protocol has been subjected to a peer review according to AstraZeneca standard procedures.

This is a multicentre, randomised, double-blind, double dummy, parallel-three group study to evaluate the efficacy and safety of D20, D40 and O20 in patients with RE.

The subjects with RE endoscopically verified grade A, B, C or D by LA classification at the time of screening, that is, within 1 week prior to initiation of the investigational product administration, will be classified based on the LA classification in grade A/B and C/D, and will be randomised to D20 group, D40 group or O20 group at the ratio of 1:1:1 in each group.

Esophagogastroduodenoscopy (EGD) will be done at Week 4 and 8 to find whether RE is healed or not. If the healing is observed at Week 4 in a subject, the subject will complete the study at the time point. The maximum duration of investigational product administration

period is 8 weeks. In addition to checking the safety throughout the study period (from the day of informed consent to the day of the last scheduled visit or withdrawal), the GERD symptoms are assessed by subjects themselves using the patient diary. Furthermore, HRQOL is assessed using QOLRAD.

A patient whose RE is healed in this study may be enrolled in the follow-on clinical study (D961HC00006) in which the efficacy and safety of D961H will be assessed on the maintenance of healed RE after the informed consent and the eligibility assessment.

All EGD images of all patients allocated the investigational products during the study period will be reviewed by the central evaluation committee (see Section 6.7) established by AstraZeneca K.K. under the blinded conditions as needed.

Figure 1 and Table 1 present the study flow chart and the schedule of the study.

Figure 1 Study flow chart

[figure not shown]

Table 1 Study plan

	Screening		Study Treatment	
		Randomisation		
Visit	1	2	3 Week 4	4 (or at discontinuation) Week 8
Days after Visit 2	-7 to 0	0	28	56
Time window (days)	-	-	±4	±4
Informed consent ¹⁾	X			
Inclusion/exclusion criteria	X	X		
Demographic data	X			
Medical/surgical history	X			
Underlying diseases	X	X		
Physical examination	X	X	X	X
Vital signs	X		X	X
Clinical laboratory tests ²⁾	X		X	X
Pregnancy test (urine) ³⁾	X			
Hp test (IgG antibody)	X ⁶⁾			
Genetic test for CYP2C19	X ⁶⁾			
QOLRAD (HRQOL)		X	X ⁸⁾	X ⁸⁾
EGD ⁴⁾	X ⁷⁾		X ⁹⁾	X
Randomisation		X		

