Dispense Patient Diary		X	X	
Review/Collect Patient Diary			X	X
Dispense investigational products		X	X	
Review/Collect returned investigational products			X	X
Review treatment compliance			X	X
Check concomitant medications	←			→
AEs ⁵⁾	←			→

1) Within 3 weeks (21 days) before visit 2 (randomisation).

2) Central laboratory is used for laboratory tests. If the results of test conducted within 2 weeks before randomisation at the laboratory test department of each participating medical institution are available, the

eligibility may be checked using these test values even if obtained before the informed consent. However, the baseline laboratory test values should be determined within 1 week before randomisation at the central laboratory.

- 3) Conducted in pre-menopausal females with a child-bearing potential.
- 4) Conducted in fasting condition.
- 5) As to serious adverse events (SAEs) and AEs resulting in discontinuation, all those that occur after informed consent are recorded in the electronic case report form (eCRF). As to the AEs other than serious or resulting in discontinuation, those that occur from the start of investigational product administration to the day of the last scheduled visit or withdrawal are recorded in eCRF.
- 6) If it is not possible to conduct it at the time of screening, the test may be conducted at any visit during the treatment period until the discontinuation or completion of this study.
- 7) If the results of test conducted within 1 week before randomisation are available, these data may be used with the consent of subject even if obtained before informed consent.
- 8) The subject fills in QOLRAD after receiving EGD.
- 9) When the healing of RE is verified by EGD, this study is completed.

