4.7.1.3 Reporting of SAEs

Investigators and other site personnel must inform appropriate AstraZeneca representatives of any SAE that occurs at his or her centre in the course of the study within 1 day (in this section, within 1 day is defined as “immediately but no later than the end of the next business day”) of

when he or she becomes aware of it (initial SAE report). This should apply whether or not the SAE is considered causally related to the investigational product or to the study procedure(s). Wherever possible, this report should be made following the “Reporting Procedure of SAEs using Web-based Data Capture (WBDC) system” described below. The principal investigator must provide detailed information to AstraZeneca in writing within 4 calendar days of the initial report. The principal investigator must notify the SAEs in writing to the head of the study site immediately.

Follow-up information on SAEs must also be reported to AstraZeneca by the investigator(s) within the same time frames. If a non-serious AE becomes serious, this and other relevant follow-up information must also be provided to AstraZeneca within 1 day as described above.

The following information is required in the initial SAE report to AstraZeneca from the investigator(s); study code, centre number, subject number, AE, seriousness, start date. The following detailed information must be sent to AstraZeneca within 1 day after it becomes available; severity, outcome (including stop date, if available), causality (investigational product and if applicable any other concomitant drug), date when a non-serious AE became serious, withdrawal of study treatment, treatment of AE, concurrent therapy (except for treatment of AE), concurrent medication (including pre-study medication if the causality of the AE cannot be assessed), date of birth, sex, other current illnesses, relevant medical history and if applicable, date and course of death.

If initial or the subsequent reports are made by means other than WBDC, necessary information on any SAEs should finally be entered into eCRF via WBDC system by the investigator(s).

For all SAEs, the AstraZeneca representative will inform the AstraZeneca Drug Safety Department of it by Day 1 and will work with the investigator(s) to compile all the necessary information and ensure that the Drug Safety Department receives a report within 4 calendar days.

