9.4 Procedures in case of pregnancy

Pregnancy itself is not regarded as an AE unless there is a suspicion that the investigational product under study may have interfered with the effectiveness of a contraceptive medication. However, the outcome of all pregnancies (spontaneous miscarriage, elective termination, normal birth or congenital abnormality) must be followed up and documented even if the subject was discontinued from the study.

All reports of congenital abnormalities/birth defects are SAEs. Spontaneous miscarriages should also be reported and handled as SAEs. Elective abortions without complications should not be handled as AEs. All outcomes of pregnancy must be recorded on the relevant pregnancy module in the eCRF.

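### New SAEs are recorded only up to the day of the last visit, so an SAE starting after the day of the final EGD falls outside the recording rule

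*Protocol*

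**What the plan says.** Section 4.7.1.2 sets the recording window for SAEs and for AEs leading to discontinuation: "those occurring during the time from informed consent to the last scheduled visit or withdrawal will be recorded at each visit". Item (e) of the same section closes the record at the same point: "The AE information will be recorded in the eCRF until the last scheduled visit or withdrawal". Section 3.1 defines the study period for safety checks in the same way, "from the day of informed consent to the day of the last scheduled visit or withdrawal".

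Some follow-up continues beyond that day:

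- Section 4.7.1.2(e), open AEs: "All AEs unresolved when the study is completed or at the time of withdrawal will be followed until the AE in concern is resolved", or until the investigator sees no further need.
- Section 4.7.1.2(a): clinically important laboratory or vital-sign abnormalities seen at completion or discontinuation.
- Section 9.4: pregnancy outcomes, which "must be followed up and documented even if the subject was discontinued from the study".

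Three other places bear on SAEs without giving an end date:

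- Section 4.7.1.1: "Note that SAEs that could be associated with any study procedure should also be reported". For such events a causal relationship is taken as given.
- Table 1, footnote 5: "As to serious adverse events (SAEs) and AEs resulting in discontinuation, all those that occur after informed consent are recorded". This sets a start and no end.
- Section 4.7.1.3 asks sites to report "any SAE that occurs at his or her centre in the course of the study".

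Section 3.4.2 tells subjects to take product after the EGD at Visits 3 and 4. It makes no exception when that visit is the subject's last.

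**The concern.** The protocol asks for SAEs that may be due to a study procedure, and EGD is an invasive procedure done at the final visit of every completer. Yet the recording rule closes on that same day. An SAE that starts the next day, whether related to the EGD or to a dose taken after it, need not be recorded under 4.7.1.2, and no planned contact would bring it to light. Safety and tolerability is a stated secondary objective. What is at stake is whether the SAE record is complete, not the comparison of healing rates.

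**Working it through.** The plan states no figure to reproduce on this point. The check sets the sections side by side and adds some day counts.

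**1. Which day is the last scheduled visit?** EGD is done at Visits 1, 3 and 4 (section 4.6.1.1). A subject healed at Visit 3 completes there (section 4.6.1.2); the others go on to Visit 4. Table 1 has no column after Visit 4. So for every completer the last scheduled visit is the day of the final EGD: nominal Day 28 (window 28 ± 4, Days 24 to 32) if healed at Visit 3, otherwise nominal Day 56 (56 ± 4, Days 52 to 60).

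**2. How long is the window after that EGD?** End of recording minus day of final EGD is 28 − 28 = 0 days, or 56 − 56 = 0 days. The difference remains 0 anywhere in the visit window, because both fall on the same visit. An event later on that day is inside the window; one with onset on the next day is outside.

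**3. Does another rule pick up a new SAE after that day?**

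- The follow-up in 4.7.1.2(e) needs an AE that is already unresolved at completion or withdrawal.
- The follow-up in 4.7.1.2(a) needs an abnormal laboratory value or vital sign seen at that time.
- Section 9.4 concerns pregnancies.
- Section 4.7.1.3 is limited to the course of the study. That phrase is not tied to a date, but section 3.1 ends the study period on the last visit day.
- Footnote 5 and section 4.7.1.1 set no end date and plan no contact.

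None of these requires a new-onset SAE after the final visit to be recorded.

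**4. Withdrawals.** Here the window ends at withdrawal, which need not be an EGD day. The 0-day statement about the final EGD is therefore made for completers.

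**5. Is drug carry-over a reason for a longer window?** Section 1.1 gives a half-life of 1.3 hours after repeated dosing in extensive metabolisers. Five half-lives are 5 × 1.3 = 6.5 hours. On that figure, drug exposure alone gives little reason to extend the window. No half-life for poor metabolisers is given.

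**6. The dose after the final EGD.** Product is first taken on Day 0, the day of dispensing (section 3.4.2). A dose on the final visit day gives Days 0 to 56 = 57 doses against 8 × 7 = 56, or Days 0 to 28 = 29 against 4 × 7 = 28. The ± 4-day window alone allows Days 0 to 52 = 53 up to Days 0 to 60 = 61 doses at Visit 4, so one dose is immaterial. The sentence does not fit with the return of all unused product at Visits 3 and 4 (section 3.8) or with completion at Visit 3 on healing.

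**The case against.** The strongest reply is that this is a consistent, explicit rule that a reviewer would merely lengthen. Every section that states an end date gives the same one. The EGD here is observational, done for grading and photographs, and the protocol neither names a delayed complication nor gives a rate. Harm done during the EGD occurs on that day and is inside the window even if diagnosed later. A site that learns of a later procedure-related SAE has section 4.7.1.1 pointing it towards reporting, with no time limit, and reporting to the sponsor is a separate duty from recording at visits.

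Most of this stands, and it narrows the point. What remains is that the one explicit end date excludes an SAE with onset after the final visit day, and that nothing is planned to find it. An undated sentence in the definitions does not override a dated recording rule.

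Several stronger readings are tempting but not supported:

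- A reader might infer that footnote 5 contradicts 4.7.1.2. It does not; it is silent on the end.
- A reader might infer that safety follow-up stops altogether. It does not; open AEs, flagged abnormalities and pregnancies are followed.
- A reader might think the final EGD is singled out. It is not; the final laboratory blood draw at the same visit has the same 0 days.
- A reader might try to use eligibility for the follow-on study D961HC00006 to count who goes unobserved. Entry is optional and that study's AE rules are not at hand, so no such count follows.
- A reader might see the final-visit dose as over-exposure. In context the sentence sets the order of test and dose, and the slip is editorial.

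**Conclusion.** The point holds as a minor one. For all completers, at most the 555 randomised, new SAEs are recorded for 0 days beyond the day of the final EGD, while the protocol elsewhere wants procedure-related SAEs reported. The effect is on completeness of SAE capture only. The rule applies equally to D20, D40 and O20, so the documents support no claim of between-arm bias, and the Week 8 healing comparison is untouched. No number of missed events is claimed, because the protocol gives no rate for them.

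The conclusion rests on two readings: that the dated rule in 4.7.1.2 governs over the undated statements in 4.7.1.1, 4.7.1.3 and footnote 5, and that the course of the study in 4.7.1.3 ends with the study period of section 3.1. If a site read 4.7.1.3 more broadly, it might report a late event it happened to hear of, but no planned contact would seek one out.

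**What to change.** In sections 4.7.1.2 and 4.7.1.3 and in Table 1 footnote 5, state one end date: SAEs with onset within a short fixed period after the last EGD or last dose, whichever is later, are recorded and reported. The sponsor sets the length; 7 days is an example and does not come from the protocol. Tell subjects at the final visit to contact the site if a serious event occurs in that period. A brief telephone call, or the first D961HC00006 contact for those who enter that study, is an optional addition.

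As an editorial change, reword section 3.4.2 so that the dose after the EGD applies only to subjects who continue treatment.

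The cost is protocol wording, an instruction at the final visit, a few more SAE records and a slightly later end of safety data collection. No visit or test is added and the sample size does not change.
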